5.1.2 Risks Associated with Worsening of Crohn's Disease

The worsening of CD may result in the use of rescue medications. In severe cases, worsening of CD may lead to hospitalization or require surgery.

At any time during the study, patients who have worsening of their CD will be permitted to receive additional therapy with corticosteroids (IV, oral, or topical). Addition of or increases in doses of immunosuppressants (i.e., AZA, 6-MP, or MTX) will also be allowed if clinically indicated by the Principal Investigator.

Rescue therapy with anti-TNF agents (including TNF inhibitor biosimilars), cyclosporine, tacrolimus, sirolimus, MMF, natalizumab, vedolizumab, anti-adhesion agents, rituximab, other lymphocyte depleting agents (except AZA and 6-MP, or equivalent), or other biological or investigational therapeutics will not be allowed in conjunction with etrolizumab because of the level of immunosuppression anticipated with the use of these agents. Patients who receive any of these prohibited rescue medications are not to receive further treatment with etrolizumab, are to complete the 12-week safety follow-up, and should then enter into Part 2 (SM) of the study.

See Section 4.4.2 and Appendix 1 for the schedule of assessments to be performed in the event of worsening of CD, which may lead to an unscheduled visit.

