5.4.6.11 Hospitalization or Prolonged Hospitalization

Any adverse event that results in hospitalization (i.e., in-patient admission to a hospital) or prolonged hospitalization should be documented and reported as a serious adverse event (per the definition of serious adverse event in Section 5.3.2), except as outlined below. The duration of hospitalization should also be noted on the eCRF.

The following hospitalization scenarios are not considered to be adverse events or serious adverse events:

- Hospitalization for respite care
- Planned hospitalization required by the protocol (e.g., for study drug administration or insertion of access device for study drug administration)
- Hospitalization for a preexisting condition, provided that all of the following criteria are met:

The hospitalization was planned prior to the study or was scheduled during the study when elective surgery became necessary because of the expected normal progression of the disease.

The patient has not suffered an adverse event.

The following hospitalization scenario is not considered to be a serious adverse event, but should be reported as an adverse event instead:

- Hospitalization that was necessary because of patient requirement for outpatient care outside of normal outpatient clinic operating hours

5.4.6.12 *Adverse Events Associated with an Overdose or Error in Drug Administration*

Study drug overdose is the accidental or intentional use of the drug in an amount higher than the dose being studied. An overdose or incorrect administration of study drug is not itself an adverse event, but it may result in an adverse event.

Any study drug overdose or incorrect administration of study drug should be noted on the Study Drug Administration eCRF.

All adverse events associated with an overdose or incorrect administration of study drug should be recorded on the Adverse Event eCRF. If the associated adverse event fulfills serious criteria, the event should be reported to the Sponsor immediately (i.e., no more than 24 hours after learning of the event; see Section 5.5.2).

5.4.6.13 **Patient-Reported Outcome Data**

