2. STATISTICAL HYPOTHESES AND SAMPLE SIZE DETERMINATION

2.1 STATISTICAL HYPOTHESES

Due to the non-comparative character of the study, no statistical tests or hypotheses are planned; all efficacy parameters will be summarized descriptively.

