2.2 SAMPLE SIZE DETERMINATION

The maximum number of patients that could be enrolled into the GA29145 OLE-SM study is approximately 1150 (i.e., all patients enrolled in Study GA29144). No formal sample size calculations were performed.

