- any segments(s) available at baseline that are not available at Week 108 will result in a non-responder status for the patient for endoscopic improvement/remission. For continuous data the patient's baseline segment score will be carried forward (BOCF) to impute the Week 104 segment score when calculating the total SES-CD score.

4.1.3.1 Endoscopic Improvement and Remission at Week 108

As endoscopy data is only collected at a common time point of Week 108 during the OLE Study GA29145, the endpoints of endoscopic improvement and endoscopic remission will be summarized only at this time point. These endpoints will be examined overall and separated by their previous endoscopic improvement status at their latest visit prior to enrollment into GA29145 i.e., at the parent study's (GA29144) Week 14 or Week 66.

The handling of patients with partially available segments is detailed in Section [4.1.3](#), this is not considered as true missing data.

Population: All patients who enrolled into Part 1 of the OLE Study GA29145.

Baseline: The original baseline value from the parent study will be used to calculate improvement.

Sub-groups:

- All patients overall and split by prior endoscopic improvement status and their prior aTNF exposure status.

Analysis 1 - Non-Responder

Missing data: Patients who are non-evaluable at Week 108 (i.e., could not have reached the maximum visit if they had remained within the program as detailed in Section 4.1.3) will be removed from the analysis. Patients who remain in Study GA29145 but are missing endoscopy scores (i.e., the assessment was not done) will be imputed as non-responders within the analysis, as LOCF is not appropriate when endoscopy data is not collected routinely.

Intercurrent events: Patients who withdraw during Study GA29145 will be set to non-responders using the composite strategy if they could have reached OLE Week 108 at the time of the clinical cut-off date had they not withdrawn from treatment. This excludes patients who withdrew from study drug on or after 15th February 2022.

Analysis 2 - As Observed

Missing data: If a patient has missing data at a visit, they will be removed from the analysis and no imputation will be performed.

Intercurrent events: No imputation will be performed for treatment withdrawals

4.1.3.2 Simple Endoscopic Score for Crohn's disease (SES-CD) score at Week 108

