4.1.3.3 CDAI Remission and Clinical Remission Every 12 Weeks

The percentage of patients in CDAI remission or clinical remission as defined in the Efficacy Derivations Section 1.3.1 will be summarized for each OLE visit for patients who entered Study GA29145. All OLE visits will be summarized until a minimum of 20 evaluable patients overall remain within the analysis (i.e., an evaluable patient either reached the visit or could have reached the visit if they had remained within the OLE).

Population: Patients who enroll into Part 1 of Study GA29145.

Baseline: The original baseline value from the parent study will be used to calculate remission, where applicable.

Sub-groups:

- Table outputs: All patients overall, split by aTNF exposure status and by OLE Day 1 CDAI remission or clinical remission status, as appropriate.
- Figure outputs: All patients overall and split by OLE Day 1 CDAI remission or clinical remission status.

Analysis 1 - Hybrid LOCF

Missing data: If patients who remain in Study GA29145 at the specified visit are missing data then LOCF will be used to impute. For visits where patients are non-evaluable (i.e. it is not possible for them to have reached the specified visit at the time of the clinical cut-off date) they will be removed from the analysis.

Intercurrent Events: Using the composite strategy in the case where patients have withdrawn from the Study GA29145, they will be set to non-responders for all visits where they are evaluable. This excludes patients who withdrew from study drug with reason being stated as “study terminated by sponsor” after 15th February 2022.

Analysis 2 - As Observed

Missing data: If a patient has missing data at a visit, they will be removed from the analysis and no imputation will be performed.

Intercurrent events: No imputation will be performed for treatment withdrawals

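### CDAI and clinical remission have no rule for Crohn's-related bowel surgery, so an operated patient who stays in Part 1 can be counted as a remitter, and no planned output counts these operations

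*SAP*

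**What the plan says.** **Remission analyses.** SAP 4.1.3.3 summarises CDAI remission (CDAI below 150) and clinical remission (stool-frequency and abdominal-pain thresholds, with neither sub-score worse than at parent-study baseline) at each 12-weekly visit. Two analyses are listed. In Hybrid LOCF, the treatment of intercurrent events is: "Using the composite strategy in the case where patients have withdrawn from the Study GA29145, they will be set to non-responders". Withdrawals after 15 February 2022 with sponsor termination as the stated reason are exempt. For patients still in the study, "If patients who remain in Study GA29145 at the specified visit are missing data then LOCF will be used to impute". The As Observed analysis imputes nothing. SAP 4.1.3 also describes a Non-Responder strategy, but 4.1.3.3 does not list it for these endpoints. Visits are shown "until a minimum of 20 evaluable patients overall remain within the analysis".

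**Surgery.** Protocol 5.1.2 states: "In severe cases, worsening of CD may lead to hospitalization or require surgery". Protocol 1.1 names avoiding surgery among the goals of treatment. Surgery is not on the mandatory discontinuation list in Protocol 4.5.2.

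**Safety recording.** Under Protocol 5.4.6.11, a hospital stay for a preexisting condition is neither an AE nor an SAE if the stay was planned before the study or was "scheduled during the study when elective surgery became necessary because of the expected normal progression of the disease", and if the patient has had no adverse event. Protocol 5.4.6.10 makes deterioration anticipated as part of Crohn's disease an AE only when the investigator judges that it worsened unexpectedly or changed in nature.

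**Endoscopy.** SAP 4.1.3 says that "any segments(s) available at baseline that are not available at Week 108 will result in a non-responder status".

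**The concern.** The SAP already treats one form of treatment failure, leaving the study, as non-response. It is silent on another that the protocol foresees. After diseased bowel has been removed, symptoms may fall below the remission thresholds because of the operation and not because of the drug. Under 4.1.3.3 that patient is scored on the post-operative value at every later visit.

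Efficacy is part of the Part 1 objective, and there is no control arm in which the same misclassification would occur and offset it. A reader of the report could not correct for it either, because nothing planned says how many patients had Crohn's surgery while they stayed in Part 1.

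**Working it through.** The plan has no figure to reproduce. SAP 2.1 says "no statistical tests or hypotheses are planned; all efficacy parameters will be summarized descriptively", and SAP 2.2 says "No formal sample size calculations were performed". The check therefore traces the rules and then sizes the effect of one patient.

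**Step 1: can an operated patient remain and be scored?** Yes. Surgery is absent from the discontinuation list (Protocol 4.5.2), from the remission definitions (SAP Table 2) and from the intercurrent events (SAP 4.1.3 and 4.1.3.3). The CDAI form in Protocol Appendix 5 has no item for resection or stoma.

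**Step 2: how are the possible courses scored?**
- Operated, stays, post-operative value meets the threshold: remitter in both analyses.
- Operated, stays, misses the next visit, last value was remission (the flare fell between 12-weekly visits): remitter in Hybrid LOCF, left out of As Observed.
- Operated, stays, misses the next visit, last value was active disease: non-remitter in Hybrid LOCF, left out of As Observed. No overstatement arises.
- Operated and withdraws: non-responder in Hybrid LOCF (unless the sponsor-termination exemption applies), with the reason shown in disposition (SAP 4.1.1).
- Operated before Week 108, with a baseline segment then unavailable: endoscopic non-responder at Week 108, while CDAI and clinical remission are still scored as in the first two courses.

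**Step 3: would the safety outputs show it?** The SAP 4.2.2 tables cover AEs, SAEs, deaths, AEs leading to discontinuation, and AEs of special interest. None covers procedures. An operation reaches them if it is linked to an AE, including unexpected worsening. Elective surgery for expected progression, with no AE, need not reach them. Protocol 4.4.2 lists procedures among the items that may be recorded at unscheduled visits, but the Appendix 1 schedule has no procedures row and no SAP output uses such data.

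**Step 4: size.** One misclassified patient shifts the proportion by 100/n percentage points:
- n = 20 (display minimum): 100/20 = 5.0
- n = 100: 100/100 = 1.0
- n = 300: 100/300 = 0.33
- n = 1150 (enrolment ceiling): 100/1150 = 0.09

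Measured against a composite rule, the overstatement at a visit is s × q. Here s is the share of evaluable patients operated on and still in Part 1, and q is the share of those counted as remitters. The documents give neither, so both are assumptions. With q from 25% to 75%:
- s = 1%: 0.25 to 0.75 points
- s = 3%: 0.75 to 2.25 points
- s = 5%: 1.25 to 3.75 points
- s = 10%: 2.5 to 7.5 points

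**The case against.** A reader might infer that Crohn's surgery appears in no output at all. The documents do not support that. The exemption in Protocol 5.4.6.11 is conditional, so urgent surgery, complications and unexpected worsening remain reportable. Withdrawal after surgery counts as non-response and appears in disposition. A segment lost before Week 108 produces an endoscopic non-response. That endoscopic rule never mentions resection, however. It covers resection only on a plain reading, it acts only at Week 108, and it does not identify surgery as the cause. What remains is that no output counts or names these operations, and that elective cases without an AE in patients who stay can go unseen.

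A reader might also infer that the bias always runs towards the drug. Measured against a composite rule, an operated patient adds either nothing or an overstatement. Measured against the patient's actual post-operative state, LOCF can err either way, because it may carry forward a pre-operative non-remission value.

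Further objections have weight. Absence from the mandatory list does not show that operated patients stayed, since Protocol 4.5.1 lets the patient or the investigator stop at any time. The study is descriptive, and SAP 4 plans a synoptic report with limited efficacy data. Added corticosteroids and immunosuppressants are permitted for worsening disease and are not intercurrent events either, so scoring patients on observed status would be a coherent choice. But the SAP does not state that choice for surgery, while it does adopt a composite rule for withdrawal. These arguments lower the priority of the point without closing the gap.

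**Conclusion.** The point holds in this form: SAP 4.1.3.3 sets only withdrawal to non-response, so a patient who has Crohn's-related bowel surgery, stays in Part 1 and then meets the threshold is counted as in remission, and no planned output counts or identifies that surgery. The likely net direction favours etrolizumab.

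The size cannot be derived from the documents. The firm figures are those per patient: 5 points at 20 evaluable patients, about 0.3 at 300 and about 0.1 at 1150. The effect per patient is therefore largest at the late visits with few patients. The 0.25 to 7.5 point range rests wholly on assumed values of s and q and should not be read as an estimate. Nor should the planned limit of about 10 years be read as the period over which cases accumulate, because the SAP reports that the sponsor terminated Part 1, with last dosing on 15 May 2022.

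**What to change.** - In SAP 4.1.3 and 4.1.3.3, name Crohn's-related bowel surgery (resection, stoma, strictureplasty) as a second intercurrent event under the composite strategy in Hybrid LOCF. Score the patient as a non-responder from the operation date to the maximum hypothetical visit, and say that this takes precedence over the sponsor-termination exemption. At minimum, run this as a sensitivity analysis and state how the main analysis handles surgery.
- Leave As Observed values in place and only flag those after surgery. Removing them would contradict that analysis's definition.
- Report a count and listing of known Crohn's operations during Part 1, drawn from AE, hospitalisation and procedure records plus a one-off site query. State that elective cases exempt under Protocol 5.4.6.11 may be incompletely ascertained.

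The cost is a few lines of SAP text, one derived date per operated patient, one listing and the query. The remission percentages may fall slightly. No new patient procedures are needed. The change concerns scoring and reporting only, and takes no position on whether operated patients should stay on treatment.

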4.2 SAFETY ANALYSES

Safety data will be assessed through descriptive summaries using the OLE population. All data available up until the clinical cut-off date (CCOD) will be reported.

Safety evaluations for the OLE population will include data from the first dose of treatment in Part 1 (OLE) until the patient completes/withdraws from the Part 1(OLE) of the study GA29145, this includes any 12-week safety follow-up data.

4.2.1 Extent of Exposure

Exposure to study treatment will be summarized by:

- treatment duration (weeks)
- number of patients receiving a dose at each visit
- number of doses received/missed for a patient

4.2.2 Adverse Events

Verbatim descriptions of AEs will be mapped to the latest version of the Medical Dictionary for Regulatory Activities (MedDRA).

Adverse events (AEs) will include all terms recorded on the AE Case Report Form (CRF) pages (except pregnancies). For each recorded AE, the term entered by the investigator describing the event (the “reported term”) will be assigned a standardized term (the “preferred term”) and assigned to a superclass term on the basis of the Medical Dictionary for Regulatory Activities (MedDRA) World Health Organization (WHO) dictionary of terms. All analyses of AE data will be performed using the preferred terms and system organ class unless otherwise specified.

For the etrolizumab program, the adverse events of special interest (AESIs) are the following:

- Systemic hypersensitivity reactions and anaphylactic and anaphylactoid reaction which will be reported using the MedDRA anaphylactic reaction Standard MedDRA Query (SMQ) algorithmic and Hypersensitivity SMQ narrow.
- Neurological signs, symptoms, and AEs that may suggest possible progressive multifocal leukoencephalopathy (see Appendices 5 and 6 of Protocol)
- Suspected transmission of an infectious agent by the study drug
- Cases of potential drug-induced liver injury that include an elevated alanine aminotransferase (ALT) or aspartate aminotransferase (AST) in combination with either an elevated bilirubin or clinical jaundice, as defined by Hy’s Law

Specific AEs listed below will also be reported:

- Serious infections
- Gastrointestinal Infections
- Opportunistic infections
- Malignancies

- Injection site reactions

A listing or, summary table (e.g., n > 10) of all AEs suspected or confirmed, and AEs associated with COVID-19 will be generated. Associated AEs are defined as all AEs reported within a time window of 7 days prior and 30 days after the confirmed COVID-19 start date (dates inclusive). Additionally, a listing of patients experiencing 'long COVID-19' will be generated. This listing will include all AEs with a duration >30 days occurring after a confirmed COVID-19 infection or a positive PCR test.

All AESIs and specific AEs will be determined using a selection of eCRF tick box or MedDRA SMQs, Adverse Events Group Terms (AEGTs), High Level Term (HLTs), High Level Group Terms (HLGTs), System Organ Class (SOC), as appropriate.

Summary tables will be generated for AEs, serious adverse events (SAEs), deaths, AEs leading to discontinuation of study drug, and AESIs. A listing will be generated for AEs, deaths, selected AESIs/specific AEs, and COVID-19 AEs. Pregnancies will be reported as narratives in the study CSR.

Summary tables of AEs will summarize the incidence of treatment-emergent AEs only. Treatment-emergent events are defined as any new AE reported on or after the first dose of OLE study drug or any worsening of an existing condition. Note that worsening of existing conditions include AEs ongoing from the parent study, GA29144. Otherwise, only AEs reported on or after the first dose of OLE study drug are included. If the onset date of the AE is prior to the day of first dose, the AE will be considered treatment emergent only if the most extreme intensity is greater than the initial intensity (i.e., the intensity for a given AE increases and its end date is on or after the date of the first dose). For all summary tables, the AEs will be sorted by SOC (in decreasing order of overall incidence) and then by preferred term (PT) (in decreasing order of overall incidence).

For OLE etrolizumab treatment, the incidence count for each AE PT will be defined as the number of patients reporting at least one treatment-emergent occurrence of the event (multiple occurrences of the same AE in 1 patient will be counted only once). The proportion of patients with an AE will be calculated as the incidence count divided by the total number of patients in the population. Each table will also present the total number of AEs reported where multiple occurrences of the same AE in an individual are counted separately.

Rate tables will be generated for selected AEs of interest. The rate per 100 patient years and 95% CIs will be summarized by treatment group and will be calculated by:

$$AE \text{ Rate (per 100 patient years)} = \frac{\text{Total number of AEs (in OLE only)}}{\text{Total number of patient years at risk (in OLE only)}} \times 100$$

where the total patient-years at risk is the sum over all patients of the time intervals (in years) from the first dose of study treatment in Part 1 (OLE) until the patient completes/withdraws from the study (including the 12-week safety follow-up, if applicable). Only treatment emergent AEs with an onset date after the first dose of open label Etolizumab in GA29145 will be included within these outputs.

All summary tables and listings will report AEs using the OLE population.

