5.3.1 Adverse Events

According to the ICH guideline for Good Clinical Practice, an adverse event is any untoward medical occurrence in a clinical investigation patient administered a pharmaceutical product, regardless of causal attribution. An adverse event can therefore be any of the following:

- Any unfavorable and unintended sign (including an abnormal laboratory finding), symptom, or disease temporally associated with the use of a medicinal product, whether or not considered related to the medicinal product
- Any new disease or exacerbation of an existing disease (a worsening in the character, frequency, or severity of a known condition), except as described in Sections [5.4.6.9](#) and [5.4.6.10](#)

- Recurrence of an intermittent medical condition (e.g., headache) not present at baseline
- Any deterioration in a laboratory value or other clinical test (e.g., ECG, X-ray) that is associated with symptoms or leads to a change in study treatment or concomitant treatment or discontinuation from study drug
- Adverse events that are related to a protocol-mandated intervention, including those that occur prior to assignment of study treatment (e.g., screening invasive procedures such as biopsies)

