5.3.2 Serious Adverse Events (Immediately Reportable to the Sponsor)

A serious adverse event is any adverse event that meets any of the following criteria:

- Fatal (i.e., the adverse event actually causes or leads to death)
- Life threatening (i.e., the adverse event, in the view of the investigator, places the patient at immediate risk of death)

This does not include any adverse event that had it occurred in a more severe form or was allowed to continue might have caused death.

- Requires or prolongs inpatient hospitalization (see Section [5.4.6.11](#))
- Results in persistent or significant disability/incapacity (i.e., the adverse event results in substantial disruption of the patient's ability to conduct normal life functions)
- Congenital anomaly/birth defect in a neonate/infant born to a mother exposed to study drug
- Significant medical event in the investigator's judgment (e.g., may jeopardize the patient or may require medical/surgical intervention to prevent one of the outcomes listed above)

The terms "severe" and "serious" are not synonymous. Severity refers to the intensity of an adverse event (rated as mild, moderate, or severe, or according to National Cancer Institute Common Terminology Criteria for Adverse Events (NCI CTCAE) criteria; see Section [5.4.4](#)); the event itself may be of relatively minor medical significance (such as severe headache without any further findings).

Severity and seriousness need to be independently assessed for each adverse event recorded on the eCRF.

Serious adverse events are required to be reported by the investigator to the Sponsor immediately (i.e., no more than 24 hours after learning of the event; see Section [5.5.2](#) for reporting instructions).

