5.4.6.4 Persistent or Recurrent Adverse Events

A persistent adverse event is one that extends continuously, without resolution, between patient evaluation timepoints. Such events should only be recorded once on the Adverse Event eCRF. The initial severity (intensity or grade) of the event will be recorded at the time the event is first reported in this study. For adverse events ongoing from the parent study, the current intensity of the event at this study start will be recorded as the initial intensity for the event in this study. If a persistent adverse event becomes more severe, the most extreme severity should also be recorded on the Adverse Event eCRF. If the event becomes serious, it should be reported to the Sponsor immediately (i.e., no more than 24 hours after learning that the event became serious; see Section 5.5.2 for reporting instructions). The Adverse Event eCRF should be updated by changing the event from "non-serious" to "serious," providing the date that the event became serious, and completing all data fields related to serious adverse events.

A recurrent adverse event is one that resolves between patient evaluation timepoints and subsequently recurs. Each recurrence of an adverse event should be recorded as a separate event on the Adverse Event eCRF.

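### An adverse event carried over from GA29144 that becomes serious or stops etrolizumab at an unchanged grade is left out of the SAE and AE-discontinuation tables

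*SAP*

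**What the plan says.** SAP 4.2.2 names the planned tables: "Summary tables will be generated for AEs, serious adverse events (SAEs), deaths, AEs leading to discontinuation of study drug, and AESIs". The next paragraph sets the filter: "Summary tables of AEs will summarize the incidence of treatment-emergent AEs only". The general definition of treatment-emergent takes in new events from the first OLE dose and worsening of existing conditions, and it states that the latter include events ongoing from GA29144. For an event with onset before the first OLE dose, the operative rule is narrower: "the AE will be considered treatment emergent only if the most extreme intensity is greater than the initial intensity". The SAP then explains this as meaning that "the intensity for a given AE increases and its end date is on or after the date of the first dose". Neither seriousness nor action taken with study drug is a criterion.

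The protocol fixes how such events are recorded. Sections 4.4.4.1 and 5.4.1 carry an ongoing parent-study event into GA29145 under its old term and start date, with its initial intensity set to the grade at OLE start. Section 5.4.6.4 keeps a persistent event on one record. If it turns serious, that record is switched from non-serious to serious, "providing the date that the event became serious".

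The protocol also treats grade and seriousness as separate attributes: "Severity and seriousness need to be independently assessed for each adverse event recorded on the eCRF" (Section 5.3.2). Its definition of an adverse event (Section 5.3.1) describes exacerbation of existing disease as "a worsening in the character, frequency, or severity of a known condition".

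**The concern.** The incidence of SAEs and the incidence of AEs leading to etrolizumab discontinuation are both named Part 1 safety outcomes (SAP 1.3.2), and SAP 4 promises that all safety outcome measures will be in the synoptic CSR. A carried-over event can never acquire an OLE onset date, so grade increase is its only way into these tables. Yet what places an event in either table is not its grade. It is that the event met a seriousness criterion, or that it caused treatment to stop. Either can happen during OLE treatment while the grade stays where it was.

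Two things follow. The two incidences can be understated and cannot be overstated by this rule. The CSR may also disagree with itself: a patient could be shown in the disposition summary as stopping treatment because of an adverse event and be absent from the AE-discontinuation table.

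**Working it through.** No sample size, power or event figure bears on the point, so there is no plan figure to reproduce. The check applies the SAP 4.2.2 rule to each possible course of an event.

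**Inputs**
- Start date of a carried-over event: the parent-study date, hence before the first OLE dose (Protocol 5.4.1).
- Initial intensity: the grade at OLE start (Protocol 5.4.1, 5.4.6.4).
- Records per persistent event: one, updated in place (Protocol 5.4.6.4).
- Entry condition for pre-OLE onset: most extreme grade above initial grade, with an end date on or after the first OLE dose (SAP 4.2.2).

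**Result by case**

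| Course of the event | Grade rises? | Treatment-emergent? | In the relevant table? |
|---|---|---|---|
| New event with OLE onset | not needed | yes | yes |
| Carried over, grade rises in the OLE | yes | yes | yes |
| Carried over, fatal | yes, to Grade 5 | yes | yes |
| Carried over, becomes serious, grade unchanged | no | no | **missing from SAE table** |
| Carried over, leads to stopping etrolizumab, grade unchanged | no | no | **missing from AE-discontinuation table** |

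**How far the other recording rules close the gap**
- *Hospitalization.* For terms not listed in CTCAE, Protocol 5.4.4 Table 2 ties hospitalization to Grade 3. A Grade 1 or 2 event that leads to admission would then usually rise in grade and be counted.
- *Life-threatening events.* The same table puts these at Grade 4, so an event at Grade 3 or below that becomes life-threatening also rises.
- *Secondary events.* Protocol 5.4.6.3 has severe or serious secondary events recorded in their own right. They then have an OLE onset.
- *Recurrences.* Under Protocol 5.4.6.4, a recurrence after resolution is a separate event.
- *Crohn's disease.* Protocol 5.4.6.10 has an unexpected worsening or change in nature recorded as an adverse event, which can produce a new record.

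For the SAE table this leaves mainly three groups: events already at Grade 3 and non-serious at OLE entry, CTCAE-listed terms whose grade does not move with the seriousness criterion, and events judged medically significant without a grade change. For the discontinuation table, Table 2 offers no comparable protection, because stopping study drug is not part of the grading.

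**What remains visible elsewhere.** The SAP plans listings separately: "A listing will be generated for AEs, deaths, selected AESIs/specific AEs, and COVID-19 AEs". The treatment-emergent limit is stated for summary tables only, so the record should appear in the AE listing. No SAE or discontinuation listing is named. SAP 4.1.1 also tabulates and lists reasons for early treatment discontinuation, with no treatment-emergent filter.

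**The case against.** The best defence has three parts.

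*The filter may not reach these tables.* The SAP lists AEs separately from SAEs and discontinuations before it restricts the AE summary tables, and Protocol 6.3.1 presents the SAE and discontinuation tables as separate, additional summaries. This reading is possible. It is the weaker one: the restriction directly follows the full list of tables, the incidence count is defined on treatment-emergent occurrences, no exemption is stated, and SAP 1 says the SAP supersedes the protocol for reporting. If an exemption is intended, the SAP should say so.

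*Grade-based emergence is a coherent convention, and nothing is hidden.* This stands for the general AE tables, which need no change. It stands less well for two tables defined by something other than grade. A listing line or a disposition row also does not supply the incidence that the SAP names as an outcome.

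*No decision depends on the counts.* The study is single-arm and descriptive. This limits the weight of the point but does not remove it, since describing safety is the study's purpose.

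Some stronger readings are tempting and are not supported:
- A reader might infer that serious events vanish from the report. They do not, because the AE listing is unfiltered.
- A reader might infer that any Crohn's disease admission following a carried-over flare is lost. That holds only if the site treats the episode as one continuous event at one grade; a complication or recurrence would be a new record.
- A reader might infer that patients entering after worsening or relapse are hit hardest. The documents do not show that these patients carry disease-related AEs across, and Protocol 5.4.6.10 calls for anticipated deterioration to be recorded only when it is unexpectedly worse or changed in nature.
- A reader might want a patient count. With 600 OLE patients, 10% to 30% carrying an event and 2% to 5% of those turning serious or stopping drug at an unchanged grade, the product runs from 600 × 0.10 × 0.02 = 1.2 to 600 × 0.30 × 0.05 = 9. Every input is invented. The product also pools two tables and ignores patients who stay in the overall count through another qualifying event.

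**Conclusion.** The point holds in a limited form. On the natural reading of SAP 4.2.2, a carried-over event that becomes serious or leads to stopping etrolizumab during the OLE at an unchanged grade is excluded from the SAE or AE-discontinuation incidence table. The direction is certain: relative to counting such events, the two incidences can only be lower. The size cannot be derived, because neither document gives the number of events carried over from GA29144 or how they evolved. It is probably small, given the recording rules that turn many such episodes into a grade increase or a new event. The conclusion rests on two assumptions: that the filter applies to all the summary tables named in SAP 4.2.2, and that sites follow the one-record rule for persistent events. Deaths are not affected. The change is worth making because it is cheap and concerns two named outcomes, but the point does not undermine the study's safety reporting as a whole.

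**What to change.** Keep the intensity rule for the general AE tables. Add one sentence to SAP 4.2.2 for the SAE and AE-leading-to-discontinuation tables only: an event with onset before the first OLE dose is also counted if the date it became serious, or the etrolizumab discontinuation attributed to it, falls on or after the first OLE dose. Events already serious at OLE entry stay out of the SAE table unless their grade rises. If these two tables were meant to be exempt from the treatment-emergent filter, state that and say which carried-over events they count.

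The data needed are largely in hand. Protocol 5.4.6.4 already collects the date an event became serious. The documents do not name the field linking an event to drug withdrawal, but the planned discontinuation table cannot be built without that attribution. Everyone in the OLE population has had at least one OLE dose, so a stop of OLE etrolizumab meets the date condition automatically.

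The cost is a small programming condition and a footnote to the two tables. The counts may be slightly less favourable. No new data collection or change to study conduct is involved.
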